7.6.5 Laboratory Data

Safety summaries based on laboratory test results include evaluation of laboratory abnormalities and changes in laboratory test values from baseline (baseline definition is provided in [Section 8.3](#)).

Laboratory abnormalities will be summarized by treatment group for double-blind period and cumulative abatacept safety period as described in [Section 7.6](#).

Laboratory abnormalities are identified using a pre-defined set of marked abnormality (MA) criteria (listed in Safety Data Convention). The frequency of subjects with laboratory MAs during treatment based on pre-specified criteria will be tabulated by treatment group, for each analyte.

Laboratory measurements and their changes from baseline will be summarized by study day and treatment group, for protocol specified analytes. Subjects who have laboratory measures at baseline and corresponding measure on at least one scheduled visit following administration of study drug will be included in the laboratory analyte assessment. Note that not all subjects have laboratory determinations for all analytes at all visits, and therefore the sample size may vary from analyte to analyte at each time point.

In addition shift tables for the following laboratory tests will be provided. The categorical classifications of these tests will be determined based on the cut points specified below and cross-tabulation of classification between baseline and each of the scheduled visits will be presented by treatment group.

Selected laboratory safety summaries will be generated for the double-blind period and the cumulative abatacept safety period separately as described in [APPENDIX 2](#).

Table 7.6.5-1: Definitions of Analytes Cut Points

Analytes (Test Code)	Cut Point
Platelet Count (PLAT)	< 100 x 10 ⁹ c/L
	≥ 100 x 10 ⁹ c/L
Alanine Aminotransferase (ALT)	< 3 x ULN
	3 - ≤ 5 x ULN
	> 5 x ULN
Aspartate Aminotransferase (AST)	< 3 x ULN
	3 - ≤ 5 x ULN
	> 5 x ULN
Neutrophils (absolute)	< 0.5 x 10 ⁹ c/L
	0.5 x 10 ⁹ c/L - ≤ 15 x 10 ⁹ c/L
	≥ 15 x 10 ⁹ c/L
G-Glutamyl Transferase (GGT)	< 3 x ULN
	3 - ≤ 5 x ULN
	> 5 x ULN

Table 7.6.5-1: Definitions of Analytes Cut Points

Analytes (Test Code)	Cut Point
Serum albumin	≤ ULNA (normal)
	> ULNA (abnormal)
██████████	█ ██████████
	██████████
██████	█ ██████████
	██████████
eGFR	< 60mL/min/1.73m ²
	60 - 89mL/min/1.73m ²
	≥ 90mL/min/1.73m ²

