3.3.1 Inclusion Criteria

1. Signed Written Informed Consent

- a) Prior to study participation, written informed consent from subjects, or in the case of minors (< 18 years), written permission (informed consent) from parents, guardians, or legally acceptable representatives must be obtained according to local laws and regulations.
- b) Assent from minor subjects should be obtained per local requirements.

2. Target Population

- a) Subjects diagnosed with TRNS (FSGS/MCD).
 - i) Pathological findings of either FSGS (excluding collapsing FSGS) or MCD on the most recent renal biopsy (renal biopsies will not be part of this study). This will be confirmed by review of the pathology report (not slides) by a central pathologist. The criteria for pathology review are in [Appendix 1](#).
 - ii) UPCR ≥ 3 at screening.

iii) Treatment Resistant or Treatment Intolerant

(1) Treatment resistant is defined as persistence of UPCR ≥ 3 in spite of therapy with any one of the following agents: corticosteroids (CS), calcineurin inhibitors (cyclosporine and tacrolimus), sirolimus, mycophenolate mofetil (MMF), mycophenolic acid (MPA), or cyclophosphamide.

(a) Duration of therapy: The duration of CS therapy required to determine treatment resistance will be 6 weeks in subjects < 18 year of age and 12 weeks for subjects ≥ 18 years. For all other agents, the minimum duration of therapy will be 16 weeks, regardless of age.

(2) Intolerance to any 2 of these agents, regardless of duration of treatment or age.

b) Subjects must be receiving either an angiotensin-converting-enzyme inhibitor (ACEi) or an angiotensin receptor blocker (ARB) or have intolerance documented in the source documents maintained at the site. If a subject is currently receiving an ACEi or ARB, the dose must be stable for at least 2 weeks, prior to randomization. Combined use of renin-angiotensin system (RAS) inhibitors will not be allowed. If aldosterone inhibitors (spiro lactone or eplerenone) or aliskiren (direct renin inhibitor) are used, they must also be at stable doses.

c) A minimal level of renal function at screening based on estimated glomerular filtration rate (eGFR) will be required.

i) ≥ 45 for subjects < 18 years (new Schwartz equation).⁴⁸

ii) ≥ 45 for subjects ≥ 18 years (CKD-EPI equation).⁴⁷

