leukocyte (WBC) count - $< 0.75 \times \text{LLN}$ or $> 1.25 \times \text{ULN}$; $< 0.8 \times$ pretreatment if pretreatment $< \text{LLN}$ or $> 1.2 \times$ pretreatment if pretreatment $> \text{ULN}$; $> \text{ULN}$ if pretreatment $< \text{LLN}$ or $< \text{LLN}$ if $> \text{ULN}$ pretreatment

lymphocytes (%) - $< 0.5 \times \text{LLN}$ or $> 2.0 \times \text{ULN}$, or $< 0.5 \times$ pretreatment if below LLN pretreatment; $> 2.0 \times$ pretreatment if above ULN pretreatment. $> \text{ULN}$ if $< \text{LLN}$ pretreatment, or $< \text{LLN}$ if $> \text{ULN}$ pretreatment

monocytes (%) - $> 2 \times \text{ULN}$; $> 2 \times$ pretreatment if pretreatment above ULN

neutrophil count (neutrophils+bands) - $< 0.67 \times$ pretreatment if pretreatment $< 1000/\text{mm}^3$; otherwise, $< 1000/\text{mm}^3$.

phosphate - $< 0.75 \times \text{LLN}$ or $> 1.25 \times \text{ULN}$; $< 0.67 \times$ pretreatment value if below LLN pretreatment, or $> 1.33 \times$ pretreatment if above ULN pretreatment; $> \text{ULN}$ if $< \text{LLN}$ pretreatment, or $< \text{LLN}$ if $> \text{ULN}$ pretreatment

platelet count - $< 0.67 \times \text{LLN}$ or $> 1.5 \times \text{ULN}$; if below normal pretreatment, $< 0.5 \times$ pretreatment value and $< 100,000/\text{mm}^3$

potassium - $< 0.9 \times \text{LLN}$ or $> 1.1 \times \text{ULN}$; $< 0.9 \times$ pretreatment if pretreatment below LLN, or $> 1.1 \times$ pretreatment if pretreatment above ULN; $> \text{ULN}$ if $< \text{LLN}$ pretreatment, or $< \text{LLN}$ if $> \text{ULN}$ pretreatment

protein, total - $< 0.9 \times \text{LLN}$ or $> 1.1 \times \text{ULN}$; $< 0.9 \times$ pretreatment if below LLN pretreatment, or $> 1.1 \times \text{ULN}$ if above ULN pretreatment; $> \text{ULN}$ if $< \text{LLN}$ pretreatment, or $< \text{LLN}$ if $> \text{ULN}$ pretreatment

SGOT and SGPT (ASAT and ALAT) - $> 3 \times$ upper limit of normal; if pretreatment above ULN, $> 4 \times$ pretreatment value

sodium - $< 0.95 \times \text{LLN}$ or $> 1.05 \times \text{ULN}$; $< 0.95 \times$ pretreatment if below LLN pretreatment, $> 1.05 \times$ pretreatment if above ULN pretreatment; $> \text{ULN}$ if $< \text{LLN}$ pretreatment, or $< \text{LLN}$ if $> \text{ULN}$ pretreatment

uric acid - $> 1.5 \times \text{ULN}$; if pretreatment above ULN, $> 2 \times$ pretreatment value

urinalysis

- a) urinary protein - > 1 gram/24 hours and $2 \times$ pretreatment value

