8 CONVENTIONS

8.1 Definitions

8.1.1 Renal Response

The renal response at a specific time point will be present if all the following criteria (composite renal index) are met at that time point:

PROTEINURIA: Reduction of baseline UPCR of $\geq 50\%$ and to less than 3.

RENAL FUNCTION: No worsening of baseline (Study Day 1) estimated glomerular filtration rate (eGFR) defined as within normal range if normal at baseline or $\geq 75\%$ baseline value if below normal at baseline.

eGFR determination will be based on the CKD-EPI⁶ for adults and the new Schwartz equation⁷ for children.

The CKD-EPI formula will be used to determine the eGFR for the adults and will be expressed as mL/min per 1.73m². The CKD-EPI formula is:

$$\text{eGFR} = 141 \times \min(\text{Scr}/k, 1)^\alpha \times \max(\text{Scr}/k, 1)^{-1.209} \times 0.993 \text{Age} \times (1.018 \text{ [if female]}) \\ \times (1.159 \text{ [if black]})$$

Where Scr is serum creatinine (mg/dL), *k* is 0.7 for females and 0.9 for males, α is -0.329 for females and -0.411 for males, min indicates the minimum of Scr/*k* or 1, and max indicates the maximum of Scr/*k* or 1, age in years.

The new Schwartz formula for use in children to determine eGFR, also expressed as mL/min per 1.73m², is:

$$\text{eGFR} = 39.1[\text{height(m)}/\text{Scr(mg/dl)}]^{0.516} \times [1.8/\text{cystatinC(mg/L)}]^{0.294} \times [30/\text{BUN(mg/dl)}]^{0.169} \times \\ [1.099]^{\text{gender}} \times [\text{height (m)}/1.4]^{0.188}$$

Gender = 1 if male and 0 if female

Normal eGFR is defined as eGFR equal or greater than the lower limit of normal (LLN) eGFR. For this study, the LLN eGFR for both adults and children is defined as 90mL/min per 1.73m².

Proteinuria assessment for primary and secondary endpoints will be obtained from 24 hour urine collections performed at baseline and Day 113. When a 24 hour collection is not possible, a single voided specimen (i.e., spot urine) will be utilized, preferably in the morning. For all other time points, the assessment will require a single void spot urine.

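### The eGFR shift table has one open class below 60 although subjects enter from 45, so it cannot record a decline from a baseline of 45-59

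*SAP*

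**What the plan says.** SAP 7.6.5 adds shift tables to the other laboratory summaries: "cross-tabulation of classification between baseline and each of the scheduled visits will be presented by treatment group". For eGFR, Table 7.6.5-1 gives three classes: "< 60mL/min/1.73m", "60 - 89mL/min/1.73m" and "≥ 90mL/min/1.73m" (per square metre). The redacted rows of that table belong to other analytes; the eGFR row is complete.

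Protocol 3.3.1 sets the screening minimum for children at "≥ 45 for subjects < 18 years (new Schwartz equation") and for adults at "≥ 45 for subjects ≥ 18 years (CKD-EPI equation").

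SAP 8.1.1 defines preserved renal function as "defined as within normal range if normal at baseline or" at least 75% of the baseline value if baseline is below normal. Normal starts at 90, so every baseline of 45-59 comes under the 75% rule.

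In the neutrophil row of the same table, the middle class runs from 0.5 up to and including 15 x 10^9/L and the top class starts at 15. Protocol Appendix 3, under "neutrophil count (neutrophils+bands"), flags counts below 1000/mm3 unless the pretreatment count was already below that.

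**The concern.** Keeping renal function is part of the primary objective, and renal-related events are adverse events of interest. A shift table is where a reader looks to see how many subjects in each arm moved to a worse renal class. Here the subjects who enter with the least renal reserve already sit in the bottom class, so the table can only show them stable or improved. For those entering at 60-89 it has one downward step, which does not separate a small loss from a near-total one. If the arms differed in renal decline among subjects with low baseline eGFR, this table would not show it.

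**Working it through.** The plan states no figure to reproduce; the point rests on class boundaries. eGFR is in mL/min/1.73 m².

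**Inputs.** Shift classes <60, 60-89, ≥90 (SAP Table 7.6.5-1). Entry ≥45 (Protocol 3.3.1). 75% rule and lower limit of normal 90 (SAP 8.1.1). Appendix 3 limits: eGFR 0.5 x pretreatment; creatinine clearance (GFR), listed under urinalysis, <0.67 x; creatinine >1.5 x.

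**Step 1: which falls change class.** Baselines on an even 0.1-unit grid:

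| Baseline | 25% fall | 50% fall | 75% fall |
|---|---|---|---|
| 45-59.9 | 0% | 0% | 0% |
| 60-89.9 | 67% | 100% | 100% |
| 90-129.9 | 75% | 100% | 100% |

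These are shares of the grid, not of expected subjects. The 67% arises because 0.75 x baseline is below 60 only for baselines under 80: (80 - 60)/(90 - 60) = 0.67. The 75% arises because 0.75 x baseline is below 90 only for baselines under 120: (120 - 90)/(130 - 90) = 0.75. In the lowest band, 45 to 33.75, 59 to 29.5 and 59 to 10 all stay below 60.

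**Step 2: a fall that the Appendix 3 limits also miss.** Take an adult going from 58 to 40.

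- Ratio: 40/58 = 0.69. This is below 0.75, so it fails the SAP rule (limit 0.75 x 58 = 43.5).
- eGFR limit: 0.5 x 58 = 29. Not reached.
- GFR limit: 0.67 x 58 = 38.9. Not reached.
- Creatinine: under the SAP's CKD-EPI formula, with sex, race and age fixed, eGFR varies as creatinine to the power -1.209 once creatinine exceeds k. At creatinine = k, eGFR is at least 141 x 0.993^age, which stays above 58 until an age of about 126, so that branch applies. Implied rise: (58/40)^(1/1.209) = 1.45^0.827 = 1.36. This is below 1.5.
- Shift table: <60 to <60, no shift.

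From a baseline of 58, every value from 38.9 to just under 43.5 behaves in this way.

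**Step 3: with the class split.** Cuts at 45, 30 and 15 are assumed, not taken from the documents. From 45-59.9, a 25% fall lands at 33.75-44.9, a 50% fall at 22.5-29.95 and a 75% fall at 11.25-14.98. All of them change class (100% against 0%). The 58-to-40 case moves from 45-<60 to 30-<45.

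**Step 4: what remains within 60-89.** A fall from 85 to 61 gives 61/85 = 0.72. It fails the 75% rule but stays in 60-89 even after the split, so a count against percentage of baseline is needed as well.

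**Step 5: where eGFR is measured and reported.** The protocol schedules eGFR at Day 1 and Day 113, then at OLE Day 169. SAP Table 9-2 marks shift tables for all three reporting periods but mean laboratory change for the double-blind period only. SAP section 9 lists two laboratory summaries for the closeout report: abnormalities and shift tables.

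**Step 6: neutrophils.** A value of exactly 15 belongs to two classes. Since 1000/mm3 equals 1.0 x 10^9/L, counts of 0.5 to <1.0, which Appendix 3 flags, share a class with normal counts.

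**The case against.** The strongest reply is that this is one descriptive table among several outputs. Laboratory changes are summarised by study day and arm, and the SAP's default statistics include quartiles, minima and maxima, so a very low value would appear. The protocol lists changes from baseline. Marked abnormalities are counted per analyte. Renal-related adverse events are tabulated with incidence rates. The 75% rule works inside renal response and complete remission. For the double-blind period much of this stands, with limits: the composite does not isolate renal loss, because failure on proteinuria, discontinuation or missing data also gives non-response; and the marked-abnormality criteria are in a convention outside the documents, so what they catch for eGFR is unknown.

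A reader might infer that the plan cannot show renal worsening from 45-59 at all. The outputs above rule that out; the limitation is this table's. A reader might also infer that Appendix 3 misses any loss short of half, for example 58 to 30 (ratio 0.517, just above the 0.5 limit). It does not: the implied creatinine rise is (58/30)^(1/1.209) = 1.72, above 1.5, and 0.517 is also under the 0.67 GFR limit. Appendix 3 does, however, guide investigators' adverse event reporting and depends on their judgement of relevance; it is not a tabulation by arm.

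It is also fair that finer cuts are a matter of choice and make cells sparse. Six classes give 36 cells instead of 9, for about 45 subjects per arm. That is a reason to pair the split with counts at limits the documents already use.

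**Conclusion.** The point holds for the eGFR row of Table 7.6.5-1. A subject with baseline 45-59 can fail the SAP's own renal-function rule, or lose half of eGFR, and still be tabulated as unchanged; from 60-89, all values below 60 share a cell. The consequence is largest after Day 113, where the planned laboratory content reduces to abnormalities with unseen criteria and the shift table, alongside adverse events.

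The size in subjects is unknown, because the documents do not give the baseline eGFR distribution. If 10% to 40% of the 90 subjects had a baseline of 45-59 (an assumption), 9 to 36 would be affected. The 58-to-40 example applies to adults, since the paediatric equation also uses cystatin C and BUN and gives no single creatinine ratio. The neutrophil faults are real but smaller. None of this touches the primary analysis, the error rate or the sample size; it is a worthwhile refinement of safety reporting.

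**What to change.** In SAP Table 7.6.5-1:

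- Split eGFR below 60, for example into 45-<60, 30-<45, 15-<30 and <15. These are reporting cuts and an assumption; apart from 45, the entry limit, the documents do not supply them.
- Write the upper classes as 60-<90 and ≥90, so that a value such as 89.5 has a class.
- Make the neutrophil classes mutually exclusive at 15 and add a cut at 1.0 x 10^9/L: <0.5, 0.5-<1.0, 1.0-<15, ≥15.

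In SAP 7.6.5, add a count by arm of subjects below 75% and at or below 50% of baseline eGFR at each scheduled eGFR visit, and mark it in Table 9-2 for all three periods. The first limit is the SAP's own. The second is Appendix 3's, which gives 0.5 x pretreatment without an inequality sign. This count captures losses within 60-89 and keeps a trivial crossing of a cut, such as 45 to 44, from being read as a large loss.

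The cost is more rows and sparser cells in a descriptive table, plus one short summary. No new data or tests are needed. The cut points should be fixed before unblinding.

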varying degrees of baseline proteinuria.^{41,42} The primary outcome used will be a composite renal index which will be used to determine the rate of renal responders. Renal responders are defined as subjects who achieve a reduction of their baseline UPCr of $\geq 50\%$ and to less than 3 with no worsening of baseline estimated glomerular filtration rate (eGFR: normal or $\geq 75\%$ baseline if below normal at baseline). Secondary and exploratory endpoints will assess associated features of nephrotic syndrome and demonstrate improvements that support the primary endpoint. These will include complete remission (UPCr ≤ 0.3 with preservation of eGFR: normal or $\geq 75\%$ baseline if below normal at baseline), patient reported outcomes (PROMIS measures), change in height as determined by standard deviation score (HSDS; z-scores) for subjects < 18 years and laboratory assessments (UPCr, serum albumin, serum total cholesterol and triglycerides).^{43,44,45}
46

Subjects who enroll must meet the criteria for TRNS (FSGS/MCD). This includes the pathological findings of either FSGS (excluding collapsing FSGS, a sub-set of FSGS seen in both HIV and non-HIV infected subjects with a more severe presentation and poor prognosis) or MCD on the most recent renal biopsy (renal biopsies will not be performed as part of this study). This will be confirmed by review of the pathology report (not renal biopsy slides) by a central pathologist.

NS will be defined by a UPCr ≥ 3 (g/g or unitless). Subjects will need to have a minimal preserved renal function as measured by eGFR (≥ 45 for children and adults (mL/min/1.73 m²) based on the CKD-EPI for adults and the new Schwartz equation for children).^{47,48}

Treatment resistance will be defined as persistence of NS in spite of therapy with either CS or other accepted agents for the required period of time (listed in the inclusion criteria) or intolerance to any 2 of these agents.

[figure not shown]

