APPENDIX 3 LABORATORY GUIDELINES: PATIENT STUDIES

Laboratory test results, which meet these criteria, and the Investigator feels is clinically relevant should be described on the Adverse Event Form. Those which are judged to be SERIOUS events require the completion of a Serious Adverse Event Form (see [Sections 6.1.1](#) and [6.3](#)).

[NOTE: LLN = lower limit of normal; ULN = upper limit of normal.]

albumin - $< 0.9 \times \text{LLN}$ or if pretreatment value is $< \text{LLN}$, $< 0.75 \times$ pretreatment

alkaline phosphatase - $> 2 \times \text{ULN}$; or if pretreatment $> \text{ULN}$, $3 \times$ pretreatment value

basophils (%) - $> 3\%$ if 0-1% pretreatment, $> 3 \times$ pretreatment value if pretreatment $> 1\%$

bilirubin

a. direct - $> 1.5 \times \text{ULN}$, or if pretreatment above ULN, $> 2 \times$ pretreatment

b. total - $> 2 \times$ upper limit of normal, or if pretreatment above ULN, $> 4 \times$ pretreatment value

blasts - > 0

blood urea nitrogen (BUN) - $> 2 \times$ pretreatment

calcium - $< 0.8 \times \text{LLN}$ or $> 1.2 \times \text{ULN}$; $< 0.75 \times$ pretreatment if pretreatment below LLN, or $> 1.25 \times$ pretreatment if pretreatment above ULN; $> \text{ULN}$ if $< \text{LLN}$ pretreatment, or $< \text{LLN}$ if $> \text{ULN}$ pretreatment

chloride - $< 0.9 \times \text{LLN}$ or $> 1.1 \times \text{ULN}$; or $< 0.9 \times$ pretreatment if pretreatment below LLN, or $> 1.1 \times$ pretreatment if pretreatment above ULN; $> \text{ULN}$ if $< \text{LLN}$ pretreatment, or $< \text{LLN}$ if $> \text{ULN}$ pretreatment

creatinine - $> 1.5 \times$ pretreatment value

eosinophils (%) - $> 3 \times$ pretreatment and $> 8\%$ if pretreatment normal; if pretreatment $> \text{ULN}$, $> 3 \times$ pretreatment

erythrocytes - $< 0.75 \times$ pretreatment value

estimated glomerular filtration rate (eGFR): $0.5 \times$ pre-treatment

glucose - $< 0.8 \times \text{LLN}$ or $> 1.5 \times \text{ULN}$; if pretreatment $< \text{LLN}$ then $< 0.8 \times$ pretreatment; if pretreatment $> \text{ULN}$ then $> 2 \times$ pretreatment; $< \text{LLN}$ if $> \text{ULN}$ pretreatment, or $> \text{ULN}$ if $< \text{LLN}$ pretreatment

hematocrit - $< 0.75 \times$ pretreatment

hemoglobin - $> 3 \text{ g/dL}$ decrease from pretreatment value

lactic dehydrogenase (LDH) - $> 1.5 \times \text{ULN}$; if pretreatment value is above ULN, $> 3 \times$ pretreatment value

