3.2 Secondary Objectives

- 1) Assess improvement in change from baseline in the level of proteinuria following treatment with abatacept compared to placebo.
 - Assess difference in mean change from baseline in Urine Protein/Creatinine Ratio (UPCR) at Day 113.
- 2) Assess improvement in serum albumin levels following treatment with abatacept compared to placebo.
 - Assess difference in mean change from baseline in serum albumin at Day 113.

- 3) Assess improvement in complete remission while maintaining renal function following treatment with abatacept compared to placebo.
 - Assess difference in percent of subjects achieving complete remission ($UPCR \leq 0.3$) with preservation of eGFR at Day 113.
- 4) Assess improvement in patient reported outcomes related to nephrotic syndrome.
 - Assess changes using the Patient Reported Outcomes Measurement Information System (PROMIS) at Day 113.
- 5) Assess the safety and immunogenicity of abatacept in subjects with TRNS.
 - Describe rates of AEs and SAEs and immunogenicity testing.
- 6) Assess the pharmacokinetics of abatacept in subjects with TRNS.
 - Describe the pharmacokinetics of abatacept.

[REDACTED]

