- Protein excretion determinations from 24 hour urine collections are considered to be more reliable than those obtained from spot urine collections. This is due primarily to the variability in the protein loss over the course of the day in chronic kidney diseases (CKD). This variability may not be similar between different forms of CKD. To help determine the degree of variability that may exist in subjects with TRNS (FSGS/MCD), UPCR are to be taken from a 24-hour urine collection on Day 1 and 113; if not possible, then from a single voided specimen. To assess the relationship between the two measurements a correlation analysis will be performed between the two measurements as an exploratory analysis. The analysis will be performed if more than 50% of subjects have both 24-hour collection and single voided specimen paired. The correlation between the 24-hour UPCR and single-void UPCR will be examined using the Pearson correlation coefficient or Kendall's Tau if either measure is not normally distributed; the estimate of the correlation coefficient and corresponding 95% CI will be provided; all subjects will be combined into one group for this analysis.
- Mean change from baseline in serum albumin at Day 113. A similar mixed model used in the above secondary endpoint will be applied for this endpoint. Adjusted mean change from baseline by treatment group and associated standard errors (SE) will be presented as well as treatment differences versus placebo with 95% confidence intervals will be provided. A summary will be provided, presenting the mean change from baseline in serum albumin at each time point in double-blind period as described above.
 - Additional summary of mean change from baseline in serum albumin at each time point during OLE will be provided. This summary will be descriptive without adjusting to stratification or baseline factors and will be presented by treatment arm.

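### The serum albumin shift table has only an upper-limit cut, so every low albumin value is tabulated as normal

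*SAP*

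**What the plan says.** SAP 7.6.5 (Laboratory Data) plans shift tables for a short list of analytes using the cut points in Table 7.6.5-1, and states that "cross-tabulation of classification between baseline and each of the scheduled visits will be presented by treatment group". For serum albumin the table has two rows. Values at or below ULNA are labelled normal. The other row reads "> ULNA (abnormal". No lower limit appears.

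ULNA is not defined in the text available. The liver-enzyme rows of the same table use ULN, and the note to Protocol Appendix 3 reads "LLN = lower limit of normal; ULN = upper limit of normal".

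SAP Table 9-2 schedules the laboratory shift tables for the double-blind period, the cumulative abatacept safety period and the open-label extension. SAP Section 9 lists them again for the closeout report.

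Two other places fix the direction that matters for albumin:

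- SAP 3.2 has as a secondary objective: "Assess improvement in serum albumin levels following treatment with abatacept compared to placebo".
- Protocol Appendix 3 flags albumin only when it is low: below 0.9 times LLN or, if the pretreatment value is already below LLN, below 0.75 times pretreatment. It has no upper criterion.

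**The concern.** Subjects enter with nephrotic-range proteinuria (UPCR of at least 3), and low serum albumin is the abnormality that goes with it. A shift table exists to show how many subjects cross the limit of normal, and in which direction. Here the only limit is the upper one, which few of these subjects should approach.

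Followed as written, the table would report nearly everyone as normal at baseline and at every later visit, in both arms. Recovery and deterioration would look the same. The one movement it would call abnormal is a large rise, and a rise is the direction the trial counts as improvement. A reader of the report would see a table implying that albumin was not disturbed in this population.

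**Working it through.** The plan gives no figure to reproduce, so the check applies the stated classes to albumin values.

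**Step 1: the logic, with no assumptions.** The SAP rule is: normal if albumin ≤ ULN, abnormal if albumin > ULN. Since LLN < ULN, any albumin < LLN satisfies albumin ≤ ULN. Every low value is therefore classed normal, whatever the laboratory's reference range.

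**Step 2: what the cross-tabulation shows.** For illustration, assume a reference range of 3.5 to 5.0 g/dL.

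| Baseline → visit (g/dL) | What happened | SAP table | Lower-limit table |
|---|---|---|---|
| 2.5 → 4.0 | recovery | normal → normal | low → not low |
| 4.0 → 2.5 | new low albumin | normal → normal | not low → low |
| 2.5 → 1.5 | further fall | normal → normal | low → low |
| 4.0 → 5.6 | rise above ULN | normal → abnormal | not low → not low |

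Under Protocol Appendix 3, the flag for a subject starting at 4.0 is 0.9 × 3.5 = 3.15 g/dL, so the fall to 2.5 is flagged. For a subject starting at 2.5 the flag is 0.75 × 2.5 = 1.875 g/dL, so the fall to 1.5 is flagged too. The SAP table shows neither.

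**Step 3: how many subjects.** The documents give no reference range, no baseline albumin distribution and no albumin entry criterion. The following are therefore assumptions: three reference ranges, and four normally distributed baselines. With Φ the standard normal distribution function:

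- share truly low = Φ((LLN − mean)/SD)
- share called normal by the SAP = Φ((ULN − mean)/SD)

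| Baseline mean / SD (g/dL) | Range 3.2–4.8: low; SAP normal | Range 3.5–5.0: low; SAP normal | Range 3.8–5.5: low; SAP normal |
|---|---|---|---|
| 2.0 / 0.6 | 97.7%; 100% | 99.4%; 100% | 99.9%; 100% |
| 2.5 / 0.7 | 84.1%; 99.9% | 92.3%; 100% | 96.8%; 100% |
| 3.0 / 0.7 | 61.2%; 99.5% | 76.2%; 99.8% | 87.3%; 100% |
| 3.5 / 0.6 | 30.9%; 98.5% | 50.0%; 99.4% | 69.1%; 100% |

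Example: for mean 2.5, SD 0.7 and range 3.5 to 5.0, (3.5 − 2.5)/0.7 = 1.43, giving 92.3% low, and (5.0 − 2.5)/0.7 = 3.57, giving 99.98% called normal. With 90/2 = 45 subjects per arm, about 0.923 × 45 ≈ 42 would have low albumin, yet essentially all 45 would sit in the normal row.

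**Step 4: the undefined abbreviation.** If ULNA was meant as a lower limit, the row would call values at or below that limit normal and values above it abnormal. The labels would then be reversed, and low albumin would still be called normal. The row is wrong on either reading.

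**The case against.** The strongest reply is that albumin is well covered elsewhere. Baseline albumin is summarised in g/dL by arm (SAP 7.3.2). Change at Day 113 is a secondary endpoint with a mixed model and confidence intervals, with results at each double-blind visit and descriptive summaries in the extension (SAP 7.5.3). Laboratory values are summarised by study day, and marked abnormalities are counted for each analyte (SAP 7.6.5). None of these uses the faulty cut. The shift table is descriptive, and SAP 7.6 rules out testing of adverse event or marked-abnormality frequencies. This limits the harm, and it stands.

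It does not rescue the row. Mean changes do not say how many subjects crossed the limit of normal. The marked-abnormality criteria are held in an external convention, and a frequency count does not cross-classify baseline against each visit.

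It is also fair that ULNA is undefined, possibly through a lost footnote mark, and that the share of subjects with low albumin cannot be known from the documents. The first point changes nothing, as Step 4 shows. The second is why a range is given. What does not depend on any assumption is that every low value is labelled normal.

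**Conclusion.** The concern holds. As specified, the albumin shift table labels every low value normal at every visit, and it runs opposite to both the protocol's own laboratory criterion and the direction of benefit in the secondary objective. That conclusion follows from LLN < ULN alone.

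The size rests on the assumed ranges and baselines: between 98.5% and 100% of subjects called normal at baseline, against 31% to 99.9% actually below LLN. The effect is limited to one row of a descriptive safety table, repeated over three analysis periods. The primary analysis and the secondary albumin analysis are untouched. It should be corrected because the planned output would be misleading and the repair is trivial.

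**What to change.** In SAP Table 7.6.5-1, replace the two albumin rows with below LLN (abnormal, low) and at or above LLN (not low). Define the abbreviation used and state the source of the reference range, by age where the laboratory's range differs.

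Two additions are optional: a lower class at below 0.9 × LLN, matching the first branch of Protocol Appendix 3, and a separate class above ULN if high values are of interest. The second branch of Appendix 3, 0.75 × pretreatment for subjects who start low, depends on each subject's own baseline. It belongs in the marked-abnormality table rather than in a fixed-cut shift table.

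The cost is one table row and one program format. No data collection, sample size or hypothesis test changes. Make the change before the double-blind database is unblinded.
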